4.2 Determination of Sample Size

It is estimated that a total of 74 patients (37 in each treatment group) will provide approximately 80% power to detect a 3-point difference between groups in the average change from baseline score for the PKAN-ADL, based on Student's t-test with alpha=0.05 (two-sided); this calculation assumes a standard deviation of 4.5 points for the change from baseline scores. Allowing for 10% attrition, a total of 82 patients will be randomized to achieve the target sample size of at least 74 patients completing the double-blind period of the study.

4.3 Planned Analysis Schedule

The primary analysis of this study will be performed after all randomized patients have either been assessed at the final visit of the 24-week double-blind treatment period or discontinued treatment and study prior to the final visit of the 24-week double-blind treatment period, and the database is locked/unblinded. The results of the double-blind treatment period, together with available long-term follow-up information in the open-label extension period at the time of the database cut-off, will form the basis of an interim CSR for submission to regulatory authorities.

4.4 Data Sets Analyzed

The following analysis sets will be defined for this study:

Double-Blind Period

Double-Blind Safety Population: The Double-Blind Safety Population will consist of all patients who receive at least 1 dose of blinded investigational product. Patients will be analyzed according to the treatment received. This population will be used for all summaries of patient accountability, demographic and baseline data, and safety information, including AE incidence, for the double-blind period of the study.

Double-Blind Full Analysis Set (FAS): The Double-Blind FAS will consist of all randomized patients with a baseline assessment and at least 1 post-baseline assessment of the primary efficacy endpoint. Patients will be analyzed in the treatment group to which

they were randomized, regardless of treatment actually received. This population will serve as the basis for all efficacy analyses for the double-blind period of the study.

Double-Blind Per-Protocol Set (PPS): The PPS will consist of all FAS patients who complete the double-blind study without any major protocol violations that could impact the interpretation of efficacy. Patients will be analyzed as randomized. This population will be used for sensitivity analyses of the primary and secondary efficacy endpoints (based on PKAN-ADL and UPDRS Part III scores). Specific protocol deviations used to define this analysis set will be finalized prior to database lock.

Open-Label Period

Open-Label Safety Population: The Open-Label Safety Population will consist of all patients who receive at least 1 dose of investigational product after entering the open-label period of the study. This population will be used for all summaries of patient accountability, demographic and Baseline data, and safety information, including AE incidence, for the open-label period of the study.

Open-Label Full Analysis Set (OL-FAS): The OL-FAS will consist of all patients with a baseline assessment and at least 1 post-baseline assessment of the PKAN-ADL in the open-label period of the study. This population will serve as the basis for efficacy analyses from the open-label period of the study.

Fosmetpantotenate Safety Population: The Fosmetpantotenate Safety population will consist of patients who received at least 1 dose of fosmetpantotenate product at any period of the study (double-blind or open-label).

The number of patients in each double-blind analysis set (Safety, FAS, and PPS) will be summarized by treatment group for the double-blind period of the study. For the open-label extension, patients in the Open-Label Safety, OL-FAS, and Fosmetpantotenate Safety Population will be summarized overall and by treatment received in the prior double-blind period. Patients excluded from any analysis set will be listed by reason.

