4.10.1.2 Handling of Dropouts and/or Missing Data

The MMRM approach used for the primary efficacy analysis accounts for data “missing at random” through a variance covariance structure. The ANCOVA models (described above) employ both the OC and LOCF methods to explore the impact of drop-outs and missing data. However, mixed models have been shown to be less biased under Missing at Random (MAR) and Missing Completely at Random (MCAR) conditions compared with LOCF or Completer analyses (Prakash, 2008).

To assess the appropriateness of the MAR assumption, additional sensitivity analyses using a tipping point approach will be used to assess how extreme and detrimental outcomes among patients with missing data must be to overwhelm the treatment effect attained in those patients who had complete data. In these analyses, the same basic analytic model will be used as in the primary analysis, but a multiple imputation approach will be implemented to allow for varying impact of missing data by incorporating a shift parameter in the imputation model. The range of values for the shift parameter will explore the varying missing data assumptions, from MAR to Missing Not at Random (MNAR), including the scenario where the imputation model is completely based on the control group (i.e., control-based imputation).

Following the approach described in Ouyang (2017), the following imputation procedures will be implemented:

1. Intermittent missing values before a discontinuation event (i.e., discontinuation of randomized therapy or early permanent dropout): The MAR assumption is reasonable for intermittent missing values before a discontinuation event since the values of the endpoint before and after the intermittent missing value are known. Imputation of intermittent missing data will be accomplished using the Markov Chain Montel Carlo (MCMC) option in SAS PROC MI by treatment group to impute intermittent missing data without a monotone missing pattern, prior to performing imputation of values following the discontinuation event.
2. Missing data following a discontinuation event (i.e., discontinuation of randomized therapy or early permanent dropout): Imputation of the post-discontinuation missing data by treatment group under the assumption of MAR using the regression option from the monotone statement of SAS PROC MI. Baseline and post-baseline scheduled visits will be used in the regression option to impute the missing values.

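### The tipping-point analysis leaves out randomised patients who have a baseline but no post-baseline PKAN-ADL, and its imputation steps do not list age group

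*SAP*

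**What the plan says.** - **Population.** SAP 4.4: "The Double-Blind FAS will consist of all randomized patients with a baseline assessment and at least 1 post-baseline assessment of the primary efficacy endpoint". The same paragraph makes this set the basis for all double-blind efficacy analyses. The only other double-blind efficacy set, the per-protocol set, is a subset of it.
- **Purpose of the tipping point.** SAP 4.10.1.2 sets out to learn "how extreme and detrimental outcomes among patients with missing data must be to overwhelm the treatment effect" seen in patients with complete data. It names no analysis set of its own.
- **Imputation.** Step 1 fills intermittent gaps by MCMC, by treatment group. Step 2 fills post-discontinuation gaps by monotone regression, also by treatment group: "Baseline and post-baseline scheduled visits will be used in the regression option to impute the missing values". Neither step lists age group.
- **Shift.** Step 4 worsens the imputed post-discontinuation values of active-arm patients by k times the treatment difference, starting at k=100%. Placebo values are not shifted.
- **Analysis model.** The imputed data go through the primary model of SAP 4.10.1, which has age group as a fixed effect. Age group is also a randomisation stratum (Protocol 8.5, SAP section 3).
- **Timing.** Full dose is reached on Day 4, and the first scheduled post-baseline PKAN-ADL is at Week 3. PKAN-ADL is also scheduled at the End of Treatment/Early Termination visit (Protocol Table 15.1-1).

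**The concern.** A tipping-point analysis asks how bad the unseen outcomes would have to be before the result is lost. The patients about whom least is known are those with nothing after baseline, and the inherited definition removes them before the question is put. The primary repeated-measures model has no change score to use for them. Multiple imputation has no such limit, because step 2 already regresses on baseline. Only active-arm values are shifted, so each omitted active-arm patient is one fewer value under stress. The reported tipping point can then look more robust than the comparison of all randomised patients would be.

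The age point is one of compatibility. An imputation model should carry the covariates of the model that analyses its output. Here the analysis step adjusts for age group, and the listed imputation predictors do not include it.

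**Working it through.** **1. The plan's own figure.** SAP 4.2: "It is estimated that a total of 74 patients (37 in each treatment group) will provide approximately 80% power". The target is 3 points between arms on PKAN-ADL change, tested at two-sided 0.05. On variability, "this calculation assumes a standard deviation of 4.5 points for the change from baseline scores". SE = 4.5 × √(2/37) = 1.046. Non-centrality = 3/1.046 = 2.87, with 72 df and critical t 1.993. Power is 80.8%, which agrees with the plan. The smallest significant difference on these assumptions is 1.993 × 1.046 = 2.09 points.

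**2. Ceiling on numbers.** "Allowing for 10% attrition, a total of 82 patients will be randomized". 82 − 74 = 8 losses across both arms, about 4 per arm. That allowance covers losses at any time. Patients with no post-baseline score would be some part of it.

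**3. Effect of the omitted patients.** Imputed under missing at random, m such active-arm patients sit on average at the active-arm mean. The shift worsens each by k × D, where D is the observed benefit. With 41 randomised per arm, the estimate becomes D × (1 − m × k/41). For D = 3 that is 3/41 = 0.07 points per patient at k=100% and 0.15 at k=200%. The p-values use SE 1.046, held fixed, and 72 df. The values of m and D are assumptions. The calculation isolates the omitted patients: shifts to dropouts already in the analysis set would come on top.

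| D (start p) | m | k | New estimate | t | p |
|---|---|---|---|---|---|
| 2.1 (0.048) | 1 | 100% | 2.05 | 1.96 | 0.054 |
| 2.4 (0.025) | 4 | 100% | 2.17 | 2.07 | 0.042 |
| 2.4 (0.025) | 2 | 200% | 2.17 | 2.07 | 0.042 |
| 2.4 (0.025) | 3 | 200% | 2.05 | 1.96 | 0.054 |
| 3.0 (0.005) | 4 | 200% | 2.41 | 2.31 | 0.024 |
| 3.0 (0.005) | 6 | 200% | 2.12 | 2.03 | 0.046 |
| 3.0 (0.005) | 7 | 200% | 1.98 | 1.89 | 0.063 |

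**4. Sensitivity to the approximation.** Dividing by 37 + m instead of 41 gives p=0.055 for the fourth row and 0.054 for the last, so the patient counts do not change. Letting the SE fall as the active arm grows gives, for three patients at D = 2.4 and k=200%, 4.5 × √(1/37 + 1/40) = 1.026 and p=0.0505. On that basis the 3-point effect needs eight patients, not seven. This ignores between-imputation variance, which would push the SE back up. Hence about 0.05 and about seven.

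**5. Age group.** A simulation compared imputation with and without age group, keeping age in the analysis model throughout. It assumed 41 per arm, 65% adults, a 2.5% loss per visit interval, age effects of 0, 2 or 4 points at Week 24, and 150 runs per scenario.

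| Dropout pattern | Mean change in Week 24 estimate (age effect 0, 2, 4) |
|---|---|
| Unrelated to age | 0.002, −0.002, 0.008 |
| Extra 5% per interval in paediatric active-arm patients | 0.031, 0.069, 0.130 |

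The SE of the treatment estimate was about 1.0 to 1.2. The Monte Carlo error of a mean change is at most about 0.301/√150 = 0.025, so the 0.031 is hardly distinguishable from zero.

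**The case against.** The strongest reply is that few patients will be affected. Withdrawing patients complete Early Termination assessments close to their last dose (Protocol 6.3.3), and these include PKAN-ADL. The analysis-set definition asks for any post-baseline assessment, not a Week 3 visit, so a patient who leaves in the first week with that assessment qualifies. Protocol 6.5.3 and 6.5.4 allow dose reduction, continued visits during interruption, and continued visits after stopping drug. All of this stands. A reader might infer that every early dropout escapes the stress test, and the documents do not support that. It is true only of patients with no post-baseline PKAN-ADL at all. How an Early Termination score enters a model confined to Weeks 3 to 24 is not spelled out, given the nominal-visit rule in SAP 6.2.2. Even so, such a patient's missing scheduled visits would fall under steps 1 to 4.

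A reader might also infer that intolerance will drive early loss. That is plausible but not documented. The Protocol synopsis takes patients who cannot tolerate the reduced dose off the study, while Protocol 6.5.3 takes them off treatment. The two passages must be reconciled, and neither gives a rate.

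It is also fair to say that a check on the primary model may coherently use that model's population, and that SAP 4.4 lists exclusions by reason, so a reader could count the omitted patients. Counting them does not show what their outcomes might do to the result.

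On age, the effect is small against the SE, age stays in the analysis step, and the SAP does not say that no other predictor may be used. The omission is worth correcting only because doing so is free.

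**Conclusion.** The point holds as a cheap improvement, not as a flaw that threatens the primary analysis. On the text, randomised patients with a baseline score and no later PKAN-ADL are outside every planned stress test. That reading rests on the general rule in SAP 4.4, because SAP 4.10.1.2 does not itself name the analysis set.

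The size depends on how many such patients there are, which the documents do not give and which may be zero. It also depends on the observed benefit. Between about 2.1 and 2.4 points, one to three active-arm patients can carry the result to or past 0.05, the upper end only at k=200%. At the 3-point design effect about seven are needed at k=200%, nearly the whole allowance of 8 for both arms. The p-values assume SD 4.5, 37 evaluable patients per arm and a fixed SE. The age omission changes the estimate by about 0.01 points, or up to about 0.13 under age-related dropout and the assumed age effects. It does not touch the primary model.

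**What to change.** In SAP 4.10.1.2, state that the tipping-point multiple imputation covers all randomised patients with a baseline PKAN-ADL, analysed as randomised. For those with no post-baseline score, impute every scheduled visit from baseline and apply the same active-arm shift as for other dropouts. Add age group to both PROC MI steps. Leave the primary repeated-measures model on the full analysis set.

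The cost is a few lines of code on data already collected, and a tipping point that may be slightly less favourable. Alpha, sample size and the primary result are unaffected. If no patient lacks a post-baseline score, the population change alters nothing. It should be written in before unblinding, so that the choice cannot be tied to the result.

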4.5 Disposition of Patients

All patients who meet the inclusion criteria for the study and sign the informed consent form will be accounted for in the disposition table.

The disposition table will present the total number of patients screened for enrollment and the number of patients in each treatment group (fosmetpantotenate and placebo) categorized as follows:

- Randomized
- Evaluated at each study visit
- Completing the double-blind treatment period

- Discontinued from treatment (by reason) for each treatment period
- Discontinued from the study (by reason) for each treatment period

A by-patient data listing of study completion information, including the timing and reason(s) for premature study withdrawal, will be presented.

Protocol deviations will be identified on an ongoing basis by the clinical study team based on the protocol deviation specification document (PDS) and assessed as “minor” or “major” in consultation with the Sponsor. This assessment will be done during the Protocol Deviation Review Meeting, which will take place when pre-determined accrual targets are met and before disclosure of randomization codes. Major deviations from the protocol that may lead to confounding of efficacy results will result in the exclusion of a patient from the per protocol set. The final determination of major protocol deviations and the exclusion of patients from each of the analysis populations will be made prior to database lock.

Unless decided otherwise during the Protocol Deviation Review Meeting, the following will be major protocol deviations:

- Major deviations of inclusion/exclusion criteria;
- Use of prohibited medication or device adjustments post-randomization that may influence the outcome of the study for the patient;
- Participation in another investigational study post-randomization without the prior written authorization of Sponsor or its designee;
- Randomization error (use of wrong medication kit or violation from randomization procedure) during the study;
- <80% or >120% compliance with study drug during the double-blind treatment period;
- Patient met withdrawal criteria but not withdrawn from treatment;
- Unblinding of study medication to blinded staff or patients;
- PKAN-ADL administration error (e.g., administration performed but due to error in translation, the instrument could not be read to the patient at Screening/Baseline Visit; unqualified rater performed the administration of the instrument)

- Failure to report Suspected Unexpected Serious Adverse Reaction (SUSAR) or Serious Adverse Event (SAE) or pregnancy; and
- Informed consent deviation (e.g., improper administration or timing).

Other possible major deviations may be identified during the protocol deviation review meetings.

Protocol deviations will be provided in a listing, sorted by treatment group, site and patient. Major protocol deviations that occur throughout the study will also be summarized by protocol deviation category and treatment group.

4.6 Demographics and Baseline Characteristics

Demographic data (including age, race, ethnicity, sex, height, weight, Body Mass Index (BMI), and Body Surface Area (BSA), pre-treatment clinical characteristics, and baseline disease assessment scores will be summarized by treatment group for the Double-Blind FAS as well as the Double-Blind Safety Population. Descriptive statistics (n, mean, SD, median, minimum, and maximum) will be presented for continuous variables. Frequency distributions (counts and percentages) will be presented for categorical variables. This table will be repeated, stratified by age group (pediatric, adult).

Similar tables summarizing demographic and baseline data will be prepared for patients in the PPS, OL-FAS as well as the Open-Label Safety Population, grouped by prior double-blind treatment assignment and overall. In the event that the FAS and Safety Population are identical for either the double-blind or open-label periods, then the tables will only be produced for the Safety Population.

A by-patient listing will be provided, presenting data collected for demographics and baseline characteristics at Screening, for patients in the Double-Blind Safety Population.

4.7 Medical History

Medical history data obtained at screening will be summarized by MedDRA System Organ Class (SOC), using Version 20.0 of the coding dictionary. These tables will be presented by treatment group for the Double-Blind Safety Population only.

PKAN-Specific Medical History will also be summarized by treatment group using the Double-Blind FAS and the Double-Blind Safety Population. This table will include age of onset, duration of illness (age at screening - age at first symptom), as well as other variables related to the disease history. This table will be repeated for patients in the Open-Label Safety Population.

By-patient listings will be provided, presenting medical history as well as PKAN-specific medical history collected at Screening for all patients in the Double-Blind Safety Population.

4.8 Prior/Concomitant Medications

Prior and concomitant medications, as well as non-drug therapies, will be coded using the World Health Organization (WHO) Drug Dictionary Sep 2018 B3 Format.

4.8.1 Prior and Concomitant Medications

Medications that start and stop prior to the date of first dose of blinded investigational product (placebo or fosmetpantotenate) medication will be classified as Prior only for the double-blind period. If a medication starts before the date of first dose of blinded investigational product and stops on or after the date of first dose of blinded investigational product, then the medication will be classified as both Prior and Concomitant for the double-blind period. Medications that were started or taken after first dose of the double-blinded investigational product and before the first dose of open-label fosmetpantotenate will be classified as Concomitant Only for the double-blind period. Medications will be classified for the open label period of the study in analogous manner.

Medications will be summarized as Prior, Concomitant, and Concomitant only, by treatment group using frequency counts and percentages within anatomical therapeutic chemical (ATC, level 2) and preferred term (PT). Medications that are specifically for PKAN maintenance will also be summarized separately. These summaries will be based on the Double-Blind Safety Population only.

Patients on chronic medications may be counted in a medication category for all periods: prior and concomitant medication for the double-blind period, and prior and concomitant medication for the open-label extension phase.

Although a patient may take more than one medication within the same ATC classification/PT, the patient will be counted only once within an ATC classification/PT for a given study phase. The same patient may contribute to two or more preferred terms in the same classification.

Non-drug therapies will be summarized in a separate table by treatment group using frequency counts and percentages within anatomical therapeutic chemical (ATC, level 2) and preferred term (PT), with no prior/concomitant classification. This summary will be based on the Double-Blind Safety Population.

A by-patient listing will be provided, which presents all medications taken by patients in the randomized population, with flags indicating if the medication is prior, concomitant, etc. for the double-blind or open-label periods. Non-drug therapies will be presented as well, in a separate listing.

4.9 Study Treatment Usage and Compliance

Duration of treatment in weeks [(date of last dose – date of first dose + 1)/7] during the double-blind period and the open-label period will be summarized for the Double-Blind and Open-Label Safety Populations, respectively. For patients in the Fostmetpantotenate Safety Population, duration of treatment following initiation of fosmetpantotenate (double-blind or open-label) will be summarized. The number and percentage of patients with dose changes or interruptions will also be presented.

Compliance is calculated as the number of actual investigational product units (capsules) administered (based on product units returned at each visit) divided by the number of expected investigational product units to be taken during the given treatment period, multiplied by 100%. The number of expected capsules for a given patient is computed by multiplying the patient's daily dosage, in 75mg powder/capsules (for oral suspension), by the daily frequency (e.g. TID) and number of days in the specified dosing period (end date - start date + 1), and then summing these values across all dosing periods within the given treatment period. In the event of a dose interruption, the expected dosage for the given interruption period would be 0 capsules. Compliance will be summarized descriptively for each treatment group, including frequency tables to indicate the number of patients who took between 80% and 120% of the doses prescribed for each treatment period.

A by-patient listing will be provided, which will present total drug accountability, along with information on compliance and dose modifications by treatment period.

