6.5.2. Dose Initiation

6.5.2.1. Double-Blind Period

The double-blind period will begin with dose escalation for Days 1 through 3, followed by the full dose (TID) starting on Day 4. Dose escalation on Days 1 through 3 will proceed as follows, based on the patient's age and weight at screening:

Patients aged 18 to 65 years and patients aged 6 to <18 years weighing ≥40 kg: On Day 1, patients will receive one 300 mg dose (in the morning); on Days 2 and 3, they will receive 300 mg twice daily (BID, at least 8 hours apart) for a total daily dose of 600 mg; and on Day 4, they will receive the full dosage of 300 mg TID (given at approximately 8 hour intervals) for a total daily dose of 900 mg.

Patients aged 6 to <18 years weighing ≥20 kg but <40 kg: On Day 1, patients will receive one 150 mg dose (in the morning); on Days 2 and 3, they will receive 150 mg BID (at least 8 hours apart) for a total daily dose of 300 mg; and on Day 4, they will receive the full dosage of 150 mg TID (given at approximately 8 hour intervals) for a total daily dose of 450 mg.

Patients aged 6 to <18 years weighing <20 kg: On Day 1, patients will receive one 75 mg dose (in the morning); on Days 2 and 3, they will receive 75 mg BID (at least 8 hours apart) for a total daily dose of 150 mg; and on Day 4, they will receive the full dosage of 75 mg TID (given at approximately 8 hour intervals) for a total daily dose of 225 mg.

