6.5.3. Dose Modification

Elective dose reductions for safety or tolerability reasons only are allowed, and only 1 time, throughout the first 6 weeks of the double-blind period of the study, according to the following schedule:

- Patients 18 to 65 years of age or 6 to <18 years of age and weighing ≥ 40 kg: the 300 mg TID dose may be reduced to 150 mg TID
- Patients 6 to <18 years of age and weighing ≥ 20 kg but <40 kg: the 150 mg TID dose may be reduced to 75 mg TID
- Patients 6 to <18 years of age and weighing <20 kg: the 75 mg TID dose may be reduced to 75 mg once daily

Patients who are unable to tolerate the reduced dose will be discontinued from treatment. The Investigator should attempt to increase the dose back to the patient's assigned fixed dose as safety and tolerability allow.

Once patients have been treated in the open-label period for at least 24 weeks, and after the second DMC review has occurred, dose increases of 1 level will be allowed for perceived lack of efficacy. Dose increases will only be allowed following consultation between the Investigator, the Medical Monitor, and the Sponsor, and only to the maximum dosage of 300 mg TID. Elective dose reductions for safety or tolerability reasons only are allowed, and only 1 time, throughout the first 6 weeks of the open-label period of the study.

Fosmetpantotenate will not in any case be used as a rescue medication.

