8.2.1.1. Study Drug Administration

Patients will be instructed to take the study drug 3 times daily (approximately 8-hour intervals) with food. The Investigator/designee will provide instructions on study drug preparation when patients have to take their dose of the study drug at home. If vomiting occurs, patients will be instructed not to take another dose of study drug and continue the study drug with their usual dosing schedule and inform the Investigator. In case the patients miss any dose of the study drug, they will be instructed not to take the missed dose immediately but follow their next scheduled dosing.

Study drug administration is outlined in [Table 1](#).

Table 1: Study Drug Administration by Dose (Capsule)

Total Daily Dose	Each Dose	Number of Capsules		Total Number of Bottles (84 capsules/bottle) Double-Blind Period (24 weeks)	Total Number of Bottles (84 capsules/bottle) Open-Label Period (278 weeks)
		Per Day	Per Dose		
225 mg	75 mg	3	1	9	70
450 mg	150 mg	6	2	17	139
900 mg	300 mg	12	4	30	278

Table 2: Study Drug Administration by Dose (Sachet – Open Label Only)

Total Daily Dose	Each Dose	Number of Sachets				Total Number of Boxes (30 sachets/box) Open-Label Period (278 weeks)
		75 mg Sachet Per Day	75 mg Sachet Per Dose	300 mg Sachet Per Day	300 mg Sachet Per Dose	
225 mg	75 mg	3	1	NA	NA	128
450 mg	150 mg	6	2	NA	NA	255
900 mg	300 mg	NA	NA	3	1	128

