8.6. Treatment Compliance

Records of investigational product used, dosages administered, and intervals between visits will be kept during the study. Drug compliance will be performed by a count of investigational product units returned at each visit. Drug compliance is calculated as the number of actual investigational product units taken (based on product units returned at each visit) divided by the number of investigational product units that should have been taken during the dosing period multiplied by 100%. Patients will be asked to return all used and unused investigational product and packaging at each visit.

Compliance with treatment will be defined as having taken between 80% and 120% (inclusive) of the doses that should have been taken during the study.

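### The expected-capsule formula in SAP 4.9 counts the daily frequency twice, so a fully adherent TID patient scores about 33% compliance instead of 100%

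*SAP*

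**What the plan says.** SAP 4.9 defines compliance as capsules administered divided by capsules expected, times 100%. The expected number is a product, worded as "daily dosage, in 75mg powder/capsules (for oral suspension), by the daily frequency (e.g. TID) and number of days in the specified dosing period", which is then added up over the dosing periods. Interruption periods count as zero expected capsules.

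Protocol 8.6 takes the units actually used "divided by the number of investigational product units that should have been taken during the dosing period", with no separate frequency factor, and sets the acceptable range at 80% to 120% inclusive.

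The protocol's daily amounts already include the frequency. Section 6.5.2.1 says of Day 4 at the highest level that "they will receive the full dosage of 300 mg TID (given at approximately 8 hour intervals) for a total daily dose of 900 mg". Table 1 in section 8.2.1.1 gives 12, 6 and 3 capsules per day for 900, 450 and 225 mg, and 4, 2 and 1 capsules per dose.

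The result feeds an analysis-set rule. SAP 4.5 opens its list with "Unless decided otherwise during the Protocol Deviation Review Meeting, the following will be major protocol deviations", and the list includes "<80% or >120% compliance with study drug during the double-blind treatment period". SAP 4.4 requires the per-protocol set to be free of major violations that could affect the interpretation of efficacy, and states: "This population will be used for sensitivity analyses of the primary and secondary efficacy endpoints".

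**The concern.** The first factor in SAP 4.9 is a daily quantity expressed in capsules, and the second is the number of doses per day. The doses per day are therefore counted once inside the first factor and again in the second. On a TID day the denominator is three times too large.

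A program that follows the text would make the compliance table and the by-patient listing wrong. It would also place essentially every adherent TID patient below the 80% limit, which is a major deviation by default. Unless the review meeting intervened, those patients would leave the per-protocol repeats of the MMRM for PKAN-ADL (SAP 4.10.1.1) and UPDRS Part III (SAP 4.10.2), and the per-protocol descriptive tables and figures. The upper limit would stop working too, because real over-use could hardly reach 120% of an inflated denominator.

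**Working it through.** **Check that Table 1 means what it says.** Total daily dose divided by 75 mg gives 900/75 = 12, 450/75 = 6 and 225/75 = 3 capsules per day. The open-label bottle counts (84 capsules per bottle, 278 weeks) follow from the per-day column:

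- 278 × 7 × 12 / 84 = 278
- 278 × 7 × 6 / 84 = 139
- 278 × 7 × 3 / 84 = 69.5, rounded up to 70

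These match Table 1, so its per-day figures already include TID dosing.

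**Inputs.** The double-blind period is 24 weeks, or 168 days. Under Protocol 6.5.2.1 there is one dose on Day 1, two on each of Days 2 and 3, and three from Day 4 (165 days).

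**Formulas.**

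- Taken under full adherence = Σ (capsules per dose × doses per day × days)
- Expected under the SAP text = Σ (capsules per day × doses per day × days)

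**Full adherence, no dose change.**

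| Level | Taken | Expected under the SAP text | Compliance |
|---|---|---|---|
| 900 mg | 4 + 2×8 + 165×12 = 2000 | 4×1 + 2×8×2 + 165×12×3 = 5976 | 33.5% |
| 450 mg | 2 + 2×4 + 165×6 = 1000 | 2×1 + 2×4×2 + 165×6×3 = 2988 | 33.5% |
| 225 mg | 1 + 2×2 + 165×3 = 500 | 1×1 + 2×2×2 + 165×3×3 = 1494 | 33.5% |

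Without the escalation days the ratio is 2016/6048 = 33.3%.

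**Effect on the limits.** True adherence of 80% to 120% would be reported as 0.80 × 33.47% = 26.8% to 1.20 × 33.47% = 40.2%. To reach a reported 80%, a patient would need 0.80 × 5976 / 2000 = 2.39 times the prescribed capsules. To exceed 120%, the patient would need 1.20 × 5976 / 2000 = 3.59 times.

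**The error is not a constant factor.** Protocol 6.5.3 provides that, for patients under 20 kg, "the 75 mg TID dose may be reduced to 75 mg once daily". A once-daily period has frequency 1 and is counted correctly, so the bias depends on the dosing history. For a fully adherent patient who stays on the reduced dose to Day 168:

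- Once daily from Day 8: taken 1 + 4 + 3×4 + 161 = 178; expected 1 + 8 + 9×4 + 161 = 206; 86.4%.
- Once daily from Day 42, the last day of the six-week window: taken 1 + 4 + 3×38 + 127 = 246; expected 1 + 8 + 9×38 + 127 = 478; 51.5%.
- Once daily from Day 43, just after the window: taken 1 + 4 + 3×39 + 126 = 248; expected 1 + 8 + 9×39 + 126 = 486; 51.0%.

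The literal rule can therefore pass a patient reduced early to once-daily dosing and fail one who took every full dose.

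**With frequency counted once.** Expected capsules are 2000, 1000 and 500 at the three levels, equal to the numbers taken, so compliance is 100% at each.

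**The case against.** The best reply is that this is a one-word slip. The sentence just before the formula in SAP 4.9 describes the denominator as the units expected to be taken, which is Protocol 8.6 in substance. Multiplying by a frequency only makes sense if the first factor is per administration, and the protocol itself uses the word dosage for the 300 mg given three times a day. Nothing shows that any program is wrong. A value near 33% in almost every patient in both arms would be noticed. SAP 4.5 lets the review meeting depart from the default list, ties exclusion to deviations that may confound efficacy, and requires the decisions before unblinding and database lock. The once-daily cases are also unusual: the protocol expects few patients under 20 kg and asks the investigator to try to restore the dose.

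Most of this stands. The intent was very probably capsules per dose, and loss of the per-protocol set is conditional. The once-daily cases show that the error varies with dosing history, not that many patients would be affected. But the general description of the denominator does not correct the formula; it confirms that the two disagree. No other part of the SAP supplies a correct computing rule. A correction made only in the program would leave an undocumented departure from a signed SAP, in a rule that decides membership of an analysis set.

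**Conclusion.** The point holds. Followed literally, SAP 4.9 gives 33.5% for full adherence over 24 weeks at every dose level (33.3% without escalation), where the protocol's definition gives 100%. This assumes that daily dosage in capsules means capsules per day, as in Table 1, and that each change of frequency starts a new dosing period.

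The reach is limited to the compliance table and listing, the compliance-based deviation flag and, unless the review meeting intervenes, the per-protocol analyses. The primary and secondary analyses on the full analysis set, the ANCOVA analyses with observed cases and LOCF, and the tipping-point analysis are unaffected. The wording should be corrected, but it does not threaten the trial's main conclusion.

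**What to change.** Reword SAP 4.9 so that expected capsules = capsules per dose × doses per day × number of days in the dosing period, summed over dosing periods. Capsules per day × days is equivalent. Either form agrees with Protocol 8.6 and Table 1. Leave the interruption rule as it is, and make the change before the protocol deviation review and database lock.

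The cost is one line of SAP text. Data collection, sample size and the primary analysis do not change.
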